Post-Procedure Care	
Immediately post-procedure for 45 days post-implant:
 
 
• All subjects must have a TTE to rule out pericardial effusion prior to discharge.
 
• Subjects receiving a Watchman device should begin/continue/resume warfarin therapy and aspirin per the product Directions for Use (DFU). [Note: Alternative vitamin K antagonists (e.g., acenocoumarol or phenprocoumon) may be used according to geographic standard of care.]
 
• Subjects receiving a WaveCrest device are required to start clopidogrel 75 mg daily and 75-100 mg aspirin daily starting 12-48 hours after the procedure (prasugrel or ticagrelor are allowable for clopidogrel intolerance, however, prasugrel is contraindicated in subjects with a history of prior stroke/TIA and both prasugrel and ticagrelor are contraindicated in subjects with a history of hemorrhagic stroke).
 
 
45 days post-implant
 
 
• At 45 days (+15/- 5 days) post-implant, a device assessment with TEE is to be performed.
 
• Warfarin cessation in the Watchman arm is per Watchman DFU but is recommended if peri-device flow by TEE is <math>\leq 5</math>mm. If an adequate seal is not demonstrated, Watchman DFU recommendation for anticoagulation should be followed until peri-device flow <math>\leq 5</math>mm is observed.
 
• When Watchman arm subjects stop warfarin, clopidogrel should be started per the product DFU.
 
• Evidence of device thrombus in either arm is recommended to be treated with a 6-week course of warfarin (+/- aspirin) and a repeat TEE. For subjects in the WaveCrest arm, clopidogrel should be stopped prior to initiating anticoagulation therapy.
 
• Subjects treated with the WaveCrest device with no evidence of device thrombus will continue dual antiplatelet therapy (DAPT) regardless of peri-device flow until 3 months post-implantation.
 
 
3 months post-implant

	Title: The WAVECREST 2 Trial  Clinical Investigational Plan	Doc. #: CHX_IP014	Rev: H
---	--	-----------------------------	------------------

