### 6.8 Follow-up 6 Month Office Visit

- Perform physical exam
- Administer QoL questionnaire (see **Quality of Life Questionnaire - SF-36**)
- Qualified trial personnel who are blinded to subject's randomization and implanted device administer the QVSFS (see **Appendix III: Questionnaire for Verifying Stroke-Free Status**); If the subject has experienced symptoms resulting in a QVSFS score  $> 0$  since their most recent follow-up, a board-certified study Neurologist blinded to subject's randomization and implanted device, to the extent possible, must evaluate the subject or otherwise provide rationale for why an in-person neurology visit and exam are unnecessary. This **Unscheduled Neurology Visit** must be completed within 14 days of the QVSFS administration or site's awareness of the onset of stroke symptoms. (See **Section 6.12** for details of Unscheduled Neurology Visit)
- For subjects in the Watchman arm, if the LAA was closed at 45 days, clopidogrel may be discontinued per the product DFU but aspirin should continue per the product DFU.
- If the LAA was not closed at 45 days and the subject remains on warfarin (Watchman arm) or DAPT (WaveCrest arm), a TEE should be repeated at this visit. Discontinuation of warfarin (Watchman arm) or P2Y12 inhibitor (WaveCrest arm) is at physician discretion but is recommended if peri-device color Doppler flow demonstrated by TEE is  $\leq 5$ mm.
- If an adequate seal is not demonstrated, warfarin (Watchman arm) or P2Y12 inhibitor (WaveCrest arm) may be continued at Investigator discretion until flow  $\leq 5$ mm is noted. Watchman subjects who continue warfarin for 6 months post-implant are not required to start clopidogrel but should remain on aspirin per the product DFU.
- Sites that routinely perform a 6-month TEE as their standard of care (SOC) may perform a TEE in all subjects at that site. This is not required for sites that do not perform a 6-month TEE as part of their SOC.
- Evidence of device thrombus is recommended to be treated with a 6-week course of warfarin (+/- aspirin) and repeat TEE.
- Record cardiac medications, including antiplatelet and anticoagulant medications
- Record adverse events, device malfunctions and protocol deviations as appropriate

	Title: The WAVECREST 2 Trial  Clinical Investigational Plan	Doc. #: CHX_IP014	Rev: H
---	--	-----------------------------	------------------

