## 6.9 Follow-up 1 Year Office Visit

- Perform physical exam
- Administer QoL questionnaire (see **Quality of Life Questionnaire - SF-36**)
- Qualified trial personnel who are blinded to subject’s randomization and implanted device administer the QVSFS (see **Appendix III: Questionnaire for Verifying Stroke-Free Status**); If the subject has experienced symptoms resulting in a QVSFS score > 0 since their most recent follow-up, a board-certified study Neurologist blinded to subject’s randomization and implanted device, to the extent possible, must evaluate the subject or otherwise provide rationale for why an in-person neurology visit and exam are unnecessary. An **Unscheduled Neurology Visit must be completed** within 14 days of QVSFS administration or site’s awareness of the onset of stroke symptoms. (See **Section 6.12** for details of Unscheduled Neurology Visit)
- Perform a TEE following the Echocardiography Protocol and submit images to ECL
- If an adequate LAA seal is observed, instruct subject to remain on aspirin dosage as assigned daily indefinitely. Table 3 summarizes the post-procedure anticoagulation and antiplatelet regimen for the duration of trial follow-up.
- If an adequate seal is not demonstrated, warfarin (Watchman arm) or P2Y12 inhibitor (WaveCrest arm) may be continued at Investigator discretion and/or until flow  $\leq$  5mm is noted.
- Evidence of device thrombus is recommended to be treated with a 6-week course of warfarin (+/- aspirin) and repeat TEE.
- Record cardiac medications, including antiplatelet and anticoagulant medications
- Record adverse events, device malfunctions and protocol deviations as appropriate

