### 6.12 Unscheduled Neurology Visit

An **Unscheduled Neurology Visit** may be triggered by any of the following:

- Subject-reported stroke/TIA;
- QVSFS score > 0;
- Subject-reported symptoms; or
- Investigator suspects a stroke during a protocol-required office visit or phone follow-up.

A board-certified study Neurologist blinded to subject’s randomization and implanted device, to the extent possible, must evaluate the following:

- The likelihood that a “yes” answer on the QVSFS or related symptoms are stroke related (this evaluation may be done over the phone or by reviewing available medical records related to a recent neurology exam).
- If there is no question of or concern for a stroke/TIA and an **Unscheduled Neurology Visit** is not required, in the opinion of the study Neurologist, rationale why this visit is not required must be documented.
- If there is any question of or concern for stroke, the subject must have an **Unscheduled Neurology Visit** within 14 days of QVSFS administration or any reported stroke/TIA. At **Unscheduled Neurology Visits** the following must be performed:
  - If stroke is suspected, the NIHSS and mRS (see **Appendix IV: Neurologic Assessments**) must be administered
  - Brain imaging must be performed (MRI unless contraindicated, then CT), unless recent brain imaging (e.g., from emergency department visit at another hospital) is available and deemed adequate by the study Neurologist, at his/her discretion.
  - If stroke is confirmed, appropriate neurology-guided investigations must be conducted to determine stroke etiology (see **Appendix I: Acronyms and Definitions** for stroke definition and etiology). The following is recommended:
    - Cervical/neck artery imaging (CTA/MTA/carotid Doppler)
    - Intracranial artery imaging (CTA/MTA/transcranial Doppler)
    - 24-hour cardiac monitoring
    - Brain imaging (MRI unless contraindicated, then CT)
    - A TEE evaluation is recommended.
      - If a TEE is indicated, perform a TEE following the Echocardiography Protocol to ascertain the mechanism of stroke and submit images to ECL
    - Subject must have a mRS re-administered 90 (+/- 15) days after any confirmed stroke
  - Any imaging files must be made available for CEC review
  - Document location of any intracranial bleeding

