f If subject had symptoms resulting in QVSFS score > 0 since their most recent follow-up at any visit or if stroke or TIA is suspected at any time during follow-up, a visit with a board-certified study Neurologist is required. The study Neurologist may waive this visit if it is based solely on QVSFS change with documented rationale.

g If stroke is suspected by the study Neurologist, administer NIHSS. Also administer mRS at the visit and 90 (+/-15) days after any confirmed stroke

h Per physician discretion if closure is not confirmed with 45-day TEE or if part of study site SOC.

i Not required for the 3-month assessment

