## 15. STATISTICAL METHODS

This section summarizes the statistical methods for the WAVECREST 2 clinical trial. A detailed statistical analysis plan describing the sample size calculations and detailed statistical methods that will be applied to the data collected in this trial will be contained in a separate document entitled **Statistical Analysis Plan** which supersedes this summary. This document will be finalized prior to un-blinding of the database and any analysis of the data

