**Descriptive Effectiveness Endpoints**

The following effectiveness endpoints will be descriptively summarized:

 	Title: The WAVECREST 2 Trial  Clinical Investigational Plan	Doc. #: CHX_IP014	Rev: H
--	--	-----------------------------	------------------

- Primary effectiveness event rate at 6 months, 3 years, 4 years and 5 years
- Composite of all stroke, systemic thromboembolism, or TIA at 45 days, 6 months, and at each annual follow-up period
- Landmark analysis of primary effectiveness endpoint from the 45-day visit to the time of each annual follow-up period
- Landmark analysis of the incidence of ischemic stroke from 6 months following device implantation and discontinuation of oral anticoagulant and dual antiplatelet therapy
- Composite of all-cause stroke at 45 days, 6 months, and at each annual follow-up period
- Incidence of thrombus on the surface of the device at 45 days, 1 year, and throughout all follow-up
- Strokes adjudicated as ischemic, hemorrhagic, or indeterminate at 45 days, 6 months, and at each annual follow-up period - see definition in **Appendix I: Acronyms and Definitions**
- Strokes adjudicated as major or minor at 45 days, 6 months, and at each annual follow-up period - see definition in **Appendix I: Acronyms and Definitions**
- Stroke adjudicated as cardioembolic in origin at 45 days, 6 months, and at each annual follow-up period - see definition in **Appendix I: Acronyms and Definitions**
- Freedom from oral anticoagulants after each protocol-required follow-up visit
- Number of devices used per subject
- Procedural success – see definition in **Appendix I: Acronyms and Definitions**
- Technical success – see definition in **Appendix I: Acronyms and Definitions**
- Device success – see definition in **Appendix I: Acronyms and Definitions**
- LAA closure rate at 45 days, 6 months, and 1 year as reported by the ECL– see definition in **Appendix I: Acronyms and Definitions**
- Procedure time, device duration, contrast usage, and fluoroscopy time

 	Title: The WAVECREST 2 Trial Clinical Investigational Plan	Doc. #: CHX_IP014	Rev: H
--	---	-----------------------------	------------------

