8.7.2 Descriptive Effectiveness Endpoints

Descriptive effectiveness endpoints will be summarized and presented as detailed below.

- **Primary effectiveness event rate at 6 months, 3 years, 4 years and 5 years**

After the primary analysis, primary effectiveness event rates will be estimated at 6 months, 3 years, 4 years and 5 years under the Bayesian piecewise exponential model. [REDACTED]

[REDACTED]

- **Composite of all stroke, systemic embolism, or TIA**

Event rates per subject-year for the composite of all stroke, systemic thromboembolism or TIA (as well as for each component) will be estimated assuming a one-parameter exponential survival model. [REDACTED]

- **Landmark analysis of primary effectiveness endpoint**

A landmark analysis of the primary effectiveness endpoint will be carried out with subject exposure start times beginning at the 45-day visit [REDACTED]

- **Landmark analysis of the incidence of ischemic stroke from 6 months following device implantation and discontinuation of oral anticoagulant and dual antiplatelet therapy**

Event rates per subject-year for ischemic stroke will be estimated assuming a one-parameter exponential survival model. [REDACTED]

- **Composite of all-cause stroke**

Event rates per subject-year for strokes of any etiology (ischemic, hemorrhagic, or other) will be estimated assuming a one-parameter exponential survival model. [REDACTED]

- **Incidence of thrombus formation on the left atrial surface of the implant**

Event rates of thrombus on the left atrial surface of the implant through all available follow-up based on TEE examination as reported by the Echocardiography Core Laboratory (ECL) will be summarized.

- **Strokes adjudicated as ischemic, hemorrhagic, or indeterminate**

Event rates per subject-year for ischemic, hemorrhagic, or indeterminate strokes will be estimated assuming a one-parameter exponential survival model. [REDACTED]

- **Strokes adjudicated as major or minor**

Event rates per subject-year for major and minor strokes will be estimated assuming a one-parameter exponential survival model. [REDACTED]

- **Strokes adjudicated as cardioembolic in origin**

Event rates per subject-year for cardioembolic strokes will be estimated assuming an exponential survival model. [REDACTED]
[REDACTED]

- **Freedom from oral anticoagulants**

The proportion of subjects free from oral anticoagulants after each scheduled follow-up visit will be summarized. [REDACTED]
[REDACTED]

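### Of the protocol's three device-thrombus summaries, SAP 8.7.2 visibly keeps only the all-follow-up rate, with no denominator and no 45-day or 1-year comparison of the arms

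*SAP*

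**What the plan says.** The protocol lists the endpoint in the same words in the synopsis and in section 15.6: "Incidence of thrombus on the surface of the device at 45 days, 1 year, and throughout all follow-up". The opening of protocol section 15 refers to a separate statistical analysis plan "which supersedes this summary".

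The thrombus item in SAP 8.7.2 reads "Event rates of thrombus on the left atrial surface of the implant through all available follow-up based on TEE examination". The readings come from the core laboratory. The item gives no fixed time, no denominator and no definition of the rate. It ends as a complete sentence with no redaction inside it. For LAA closure, the other TEE-based endpoint, the same SAP section keeps 45 days, 6 months and 1 year and restricts the analysis to TEEs evaluated by the core laboratory.

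On imaging, the protocol says:

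- 45 days (synopsis, post-procedure care): "At 45 days (+15/- 5 days) post-implant, a device assessment with TEE is to be performed".
- 6 months (Table 4 footnote): "Per physician discretion if closure is not confirmed with 45-day TEE or if part of study site SOC". Section 6.8 adds: "Sites that routinely perform a 6-month TEE as their standard of care (SOC) may perform a TEE in all subjects at that site".
- 1 year (section 6.9): "Perform a TEE following the Echocardiography Protocol and submit images to ECL".
- After a confirmed stroke (section 6.12): "A TEE evaluation is recommended".
- After a thrombus finding (sections 6.6 and 6.8 to 6.10): a repeat TEE is recommended.
- No TEE is scheduled after 1 year. Subjects without an implant have no follow-up TEE (Table 4).

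**The concern.** A rate over all follow-up depends on how often a subject is imaged as well as on how often thrombus forms. Only the 45-day and 1-year TEEs are common to all implanted subjects. The rest are triggered by leak, site habit or clinical events. One pooled figure therefore combines subjects with different chances of detection.

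It also removes timing. Up to day 45 the two arms take different antithrombotic drugs (synopsis; Table 3). The 45-day TEE is the first scheduled look after implant, before any scheduled TEE can lead to treatment for thrombus. A summary that does not separate that visit cannot show whether the two device-plus-drug strategies differ early. The question matters to this trial: protocol section 3.2 lists less thrombus on the atrial face as a possible WaveCrest benefit, and section 5.1 says the membrane there is designed to resist it.

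**Working it through.** The documents give no planned thrombus rate, sample size or power for this endpoint, so there is no figure to reproduce. The check is a comparison of texts, followed by illustrations on assumed values.

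**Step 1. Time points side by side.**

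| Summary | Protocol (synopsis, 15.6) | Visible SAP 8.7.2 |
|---|---|---|
| Thrombus at 45 days | yes | absent |
| Thrombus at 1 year | yes | absent |
| Thrombus, all follow-up | yes | yes |
| Denominator | not stated | not stated |
| Surface | device | left atrial face of the implant |

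The SAP keeps one of the three summaries.

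**Step 2. How far can unequal imaging move the pooled rate?** Assume each TEE finds thrombus with probability p, independently between looks. With k looks, the probability of detection is 1 − (1 − p)^k.

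| p | two looks | three looks |
|---|---|---|
| 1% | 2.0% | 3.0% |
| 2% | 4.0% | 5.9% |
| 3% | 5.9% | 8.7% |

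For scale, protocol section 2.7 reports thrombus on follow-up TEE in 2 of 92 commercial WaveCrest cases (2.2%).

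Now suppose 5% of one arm has the extra 6-month TEE. At p = 2% its pooled rate is 0.95 × 0.0396 + 0.05 × 0.0588 = 4.06%.

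- If 15% of the other arm has it: 0.85 × 0.0396 + 0.15 × 0.0588 = 4.25%, a ratio of 1.05.
- If 30% has it: 0.70 × 0.0396 + 0.30 × 0.0588 = 4.54%, a ratio of 1.12.

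The ratios are nearly the same at p = 1% and 3%. With identical true risk, the distortion is modest unless extra imaging is very unbalanced.

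**Step 3. What if the rate is per subject-year?** Neighbouring SAP items use subject-years; this one does not say. A 4% cumulative risk found by 1 year would read 4/1 = 4.0, 4/2 = 2.0 or 4/5 = 0.8 per 100 subject-years at 1, 2 or 5 years of follow-up, because no later TEE is scheduled. The figure would depend on when the analysis is run.

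**Step 4. What a 45-day comparison would offer.** SAP 8.5 gives 1250 to 1550 randomized 1:1, so 625 to 775 per arm. The 95% half-width for a difference is 1.96 × √[p1(1 − p1)/n + p2(1 − p2)/n].

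- Assumed 3% v 1%: the difference is 2.0 points. The half-width is 1.96 × √(0.0390/625) = 1.5 points, or 1.96 × √(0.0390/775) = 1.4 points.
- Assumed 2% v 1%: the difference is 1.0 point. The half-width is 1.96 × √(0.0295/625) = 1.3 points, or 1.96 × √(0.0295/775) = 1.2 points.

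These use all randomized subjects. The number with an evaluable TEE will be smaller and the intervals somewhat wider; the documents give no expected TEE completeness. A difference of about 2 points would be visible at 45 days, and a difference of 1 point would not be settled.

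**The case against.** **Supersession is narrower than it looks.** Only protocol section 15 gives way to the SAP. The synopsis stands outside it and still lists all three summaries. This is correct, and it means the two documents disagree; it does not supply the missing analysis in the SAP. The all-follow-up rate was also one of the protocol's own three, so the SAP has not substituted a new endpoint.

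**Silence may not mean omission.** The SAP speaks of rates in the plural. Part of the general paragraph of SAP 8.7 is redacted, and the list of tables is not shown. Visible text for several stroke and mortality endpoints also lacks the protocol's time points. This stands as a limit on certainty. Those other items, however, are mostly followed by redactions, whereas the thrombus item is complete as printed, and the LAA closure item states its times openly.

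**The imaging argument is limited.** The TEE schedule is the same by design in both arms. Exposure differs between subjects, and between arms only if closure, implant success, stroke or site practice differ. Repeat TEEs after a thrombus cannot add new cases. A reader might infer that the pooled rate materially biases the comparison, or that later events would cancel an early difference. Step 2 does not support the first, and nothing in the documents suggests the second.

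**Day 45 is not unique.** The 1-year TEE is scheduled for all implanted subjects too. Table 3 shows the regimens still differ at 3 months, with clopidogrel in the Watchman arm on stopping warfarin and none in the WaveCrest arm.

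**The SAP's surface wording may be the better one.** A reader might infer that narrowing to the left atrial face is an error. Protocol section 5.1 says the foam facing the appendage is designed to promote thrombus, so the narrower wording separates unwanted from intended thrombus.

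**Conclusion.** The point holds in a limited form. The visible SAP text omits two of the three thrombus summaries that the protocol specifies and states no denominator. The remaining rate mixes unequal imaging between subjects and cannot show whether the arms differ at 45 days while on different drugs. The timing loss follows from the text alone and needs no assumed rate. The imaging effect rests on assumed values: a factor of about 1.05 to 1.12 if 15% to 30% of one arm against 5% of the other has an extra TEE.

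A reader should not infer that trial success or its error rate is touched. SAP 8.7 makes these endpoints descriptive, with no labeling indication sought. Nor is the information lost: scheduled TEEs go to the core laboratory, so fixed-time rates stay recoverable. The conclusion assumes that no redacted passage or table shell restores the time points. It concerns the interpretation of device safety and agreement between the documents, and it merits correction because the remedy is nearly free.

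**What to change.** In SAP 8.7.2:

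1. Add device-thrombus rates at 45 days and at 1 year, by arm with 95% confidence intervals, among implanted subjects with a core-lab-evaluable scheduled TEE at that visit. Show the number evaluable beside the number implanted.
2. Keep the all-follow-up rate as a further line, split into thrombus first found on scheduled and on unscheduled TEEs. State whether it is a proportion or a rate per subject-year.
3. Use one surface definition in both documents. The SAP's left atrial surface may stay, with the protocol aligned to it.

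If redacted text already sets these times, a cross-reference in the thrombus item is enough for the first change. The data are already collected. The cost is a few extra table rows and the programming for them.

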8.7.3 Procedural Results

The following procedural data, which are not trial endpoints, will be summarized by randomized arm for the mITT population. Summary statistics (n, mean, standard deviation, median, minimum, maximum, and 95% confidence interval) will be provided.

- Device deployment duration
- Procedural duration
- Catheterization lab duration
- Anesthesia duration
- Contrast volume

[Redacted text block]

[Large redacted text block]

[Redacted text block]

8.10 Sensitivity Analyses

Sensitivity analyses will be performed for the primary results that will be used to support a pre-market approval application. [Redacted text]

[Redacted text block]

[Redacted text block]

[Redacted text block]

[Redacted text block]

8.11 [Redacted section header]

[Redacted text block]

- | [Redacted list item]
- | [Redacted list item]
- | [Redacted list item]
- | [Redacted list item]
- | [Redacted list item]
- | [Redacted list item]
- | [Redacted list item]

[Redacted text block]
